5.2.3. MATCHING CRITERIA

A total of 5 patients will be matched to 1 patient of the PUL cohort for each procedure (TURP, HLE, GLV) according to age, date of the procedure (same month) and a high dimensional disease risk score (hDRS) based on the one-year SNDS information before the surgical procedure. The Disease Risk Score (DRS) estimates the probability of complications occurrence in the absence of the surgery of interest (PUL). DRS will be computed from a multivariable logistic regression model using a large set of variables collected during the one-year period among the SNDS cohort.

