11. STATISTICAL ASPECTS

11.1. CALCULATION OF STUDY SIZE

In the SNDS, the study size will depend on the number of patients initially recruited. The expected number of patients will thus be for:

- **PUL Cohort:** 80 patients with PUL;
- TURP/Laser Cohort: 80 patients for the TURP or laser surgery
- **SNDS Cohort:** 1200 patients distributed between 400 matched TURP patients, 400 matched HLE patients and 400 matched HLV patients.

80 patients (in each of the PUL and TURP cohorts) will allow 95% confidence intervals with a precision:

- between 7% and 11% for observed proportions between 10% and 50%
- between 13% and 26% for observed means with coefficient of variation between 0.6 and 1.2.

Furthermore, 80 patients in each PUL and TURP cohorts is largely enough to answer to the primary economic objective (cost-effectiveness ratio, expressed as incremental cost/avoided complications) with a power of 80% and an alpha risk of 5%. In fact, according to the Glick formula¹, the needed number to treat to answer this question is about 40.

400 patients in each of the 3 subgroups of the SNDS cohort will allow 95% confidence intervals with a precision:

- between 3% and 5% for observed proportions between 10% and 50%,
- between 6% and 12% for observed means with coefficient of variation between 0,6 and 1,2.

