11.2. STATISTICAL METHODS EMPLOYED

11.2.1. GENERALITIES

Statistical analysis will be performed using SAS® software (SAS Institute, latest current version, North Carolina, USA). Qualitative and ordinal variables will be summarized by frequencies and proportions of each modality, taking into account missingness as a modality. Continuous variables will be summarized by size, number of patients with missing data, arithmetic mean, standard deviation, median, interquartile ranges and extreme values. Confidence intervals will be estimated using Normal approximation for quantitative and qualitative relevant parameters, or bootstrapping method for costs when count < 100 patients.

Standardized mean differences (*Rosenbaum*, *Rubin*, 1985) will be estimated to measure the effect size of quantitative and qualitative baseline characteristics between groups (PUL and TURP cohorts, matched patients of PUL and SNDS cohorts).

For confidence intervals, 2-sided confidence level of 95% will be used. For all tests, a 2-sided significance level of 5% will be used:

- Proportions will be compared between two independent groups using Pearson's Chi-2 test (or Fisher's exact test when expected counts are < 5)
- Means will be compared between two independent groups using Student's t-test when normal distribution is followed (or Mann-Whitney's test when normal distribution is not followed)
- Occurrence of events (retreatment, urinary symptoms) will be estimated across time using Kaplan-Meier estimator and compared between groups with logrank test.
- Adjusted comparisons between PUL and the TURP/Laser cohorts and between PUL and SNDS cohorts will be
 performed in intention-to-treat analysis using linear regression model when it involves quantitative variables,
 and using logistic regression model adjusted on potential confounders when it involves qualitative variables.

[figure not shown]
A Statistical Analysis Plan (SAP) will be developed and will be validated before the analyses.

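### The PUL v SNDS linear regressions (80 v 400 per procedure, or 80 v 1200 pooled) make no provision for unequal variance, so default standard errors would be wrong if the cohorts' spreads differ

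*Protocol*

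**What the plan says.** Protocol section 11.2.1 gives two layers of analysis for quantitative variables.

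- **Unadjusted:** "Means will be compared between two independent groups using" Student's t if the data are normal, and Mann-Whitney if they are not.
- **Adjusted, PUL v TURP/laser and PUL v SNDS:** "performed in intention-to-treat analysis using linear regression model when it involves quantitative variables". The data analysis part of the protocol summary repeats this. Neither place names a variance estimator.

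The same section sets the test level: "For all tests, a 2-sided significance level of 5% will be used". It uses the Normal approximation for confidence intervals, with a bootstrap for costs when the count is below 100, and it announces a SAP.

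Section 11.1 gives the sizes: "80 patients with PUL", "80 patients for the TURP or laser surgery" and "1200 patients distributed between 400 matched TURP patients, 400 matched HLE patients and 400 matched HLV patients". Section 5.2.3 gives the ratio: "A total of 5 patients will be matched to 1 patient of the PUL cohort for each procedure". Section 11.1 also states the precision for the 80-patient cohorts as "between 13% and 26% for observed means with coefficient of variation between 0.6 and 1.2", and it uses the same range of coefficients of variation for the SNDS subgroups of 400.

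Section 1.3 says that the SNDS holds no clinical information on functional results. The quantitative PUL v SNDS outcomes are therefore essentially costs and consumption.

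**The concern.** A linear regression with its default standard error estimates one residual variance for both groups. At 1:5 or 1:15 that variance comes almost entirely from the SNDS men, yet most of the uncertainty in the difference comes from the 80 PUL men. If PUL costs are more variable than SNDS costs, the standard error is too small and the test rejects too often. If they are less variable, the interval is too wide and a real difference may be missed.

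This would arise even with independent patients, so it is separate from the question of how the matching is handled. What is at stake is the complementary SNDS comparison of costs and consumption. Section 1.3 relies on it to strengthen the clinical comparison and to supply statistical power, and the results are meant to support reimbursement.

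**Working it through.** **1. The plan's own precision figures.** The half-width for a mean, relative to that mean, is 1.96 × CV / √n.

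- n=80: 1.96 × 0.6 / √80 = 13.1%; 1.96 × 1.2 / √80 = 26.3%.
- n=400: 5.9% and 11.8%.

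These reproduce section 11.1 (13–26% and 6–12%). The proportions also reproduce: 6.6–11.0% at n=80 and 2.9–4.9% at n=400. The protocol states no type I error or interval width for PUL v SNDS.

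**2. Inputs.** n1 = 80 (PUL), and n2 = 400 per procedure or 1200 pooled (section 11.1). Alpha is 0.05, two-sided (section 11.2.1). The ratio of PUL SD to SNDS SD is **not given**. I assume 0.5 to 2.0, which is what the two ends of the shared CV range (0.6 and 1.2) allow at equal means.

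**3. Formula.** The pooled variance is sp² = [(n1−1)s1² + (n2−1)s2²] / (n1+n2−2). The ratio of the default to the true standard error is

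R = √[sp²(1/n1 + 1/n2)] / √[s1²/n1 + s2²/n2].

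R is the relative interval width, and the actual type I error is 2[1 − Φ(1.96R)].

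**4. Two cases in full, n2 = 400.**

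- PUL SD half the SNDS SD (0.6 v 1.2): sp² = (79×0.36 + 399×1.44)/478 = 1.2615. Default SE = √(1.2615×0.015) = 0.1376. True SE = √(0.0045+0.0036) = 0.0900. R = 1.53.
- PUL SD twice the SNDS SD (1.2 v 0.6): sp² = (79×1.44 + 399×0.36)/478 = 0.5385. Default SE = √(0.5385×0.015) = 0.0899. True SE = √(0.018+0.0009) = 0.1375. R = 0.654, so type I error = 2[1 − Φ(1.281)] = 20.0%.

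**5. The range.**

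| PUL SD / SNDS SD | R, n2=400 | Type I, n2=400 | R, n2=1200 | Type I, n2=1200 |
|---|---|---|---|---|
| 0.50 | 1.53 | 0.3% | 1.79 | <0.1% |
| 0.67 | 1.30 | 1.1% | 1.42 | 0.5% |
| 0.80 | 1.16 | 2.3% | 1.22 | 1.7% |
| 0.91 | 1.07 | 3.7% | 1.09 | 3.3% |
| 1.00 | 1.00 | 5.0% | 1.00 | 5.0% |
| 1.10 | 0.94 | 6.6% | 0.92 | 7.1% |
| 1.25 | 0.86 | 9.1% | 0.82 | 10.7% |
| 1.50 | 0.77 | 13.2% | 0.70 | 16.8% |
| 2.00 | 0.65 | 20.0% | 0.56 | 27.4% |

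At 80 v 80 (PUL v TURP/laser), R = 1.00 and type I error is 5.0% at every SD ratio.

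**6. Simulation check** (5000 runs, equal means, independent patients, no covariates). With gamma data at SD ratio 2, the pooled test rejected in 20.2% (n2=400) and 27.1% (n2=1200) of runs. At ratio 0.5 it rejected in 0.3% and 0.1%. The unequal-variance (Welch) test gave 4.8–6.5% with gamma data and 4.7–5.1% with normal data at the same ratios.

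**The case against.** The strongest reply is that the protocol never specifies an ordinary or equal-variance regression. It names a linear regression and announces a SAP, and robust standard errors would fit the present text. That stands: nothing written is strictly wrong, and the estimator could properly be left to the SAP. But the section already goes into interval methods. It makes the Normal approximation the default and limits the bootstrap to counts below 100. These regressions contain 480 or 1280 men. One could read the count as the 80 in the PUL group, but the text does not say so. Followed literally, the section leads to the default standard error.

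Several stronger readings are tempting but not supported.

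- **That Student's t will be misapplied to skewed costs.** Section 11.2.1 sends non-normal data to Mann-Whitney. A normal variable with CV 0.6 to 1.2 would put 4.8% to 20% of values below zero, which costs cannot have, so Student's t would not be used on them. The adjusted regression has no such switch.
- **That the protocol expects the spreads to differ.** Section 1.2 says that complications are costly, which concerns the level of cost. Section 11.1 gives one CV range for all cohorts. Nothing states a difference in SD, or its direction: fewer costly complications could narrow the PUL spread, while earlier relapse (section 1.4) could widen it.
- **That 1.8 times or 27% is the expected error.** Both figures need a twofold SD ratio and all 1200 SNDS men pooled. Sections 1.3 and 5.2.3 point to comparison by procedure, at 80 v 400.

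The calculation is also for an unadjusted contrast of independent patients. Covariates and matching would change the residual variances, so the figures are a guide to size.

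**Conclusion.** The point holds as an inexpensive improvement to the PUL v SNDS regressions. With default model-based standard errors, moderate differences in spread already matter at 80 v 400: type I error is about 9% at an SD ratio of 1.25 and 13% at 1.5, and intervals are about 1.16 times too wide at 0.8. The extremes of the stated CV range give 20% type I error or intervals 1.5 times too wide. Pooling all 1200 raises these to 27% and 1.8. All of this is conditional on SDs that the protocol does not state, and the error vanishes if they are equal.

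The scope is limited to the complementary SNDS analysis. The 80:80 comparison is essentially unaffected, and so is the primary cost-effectiveness ratio, whose interval section 11.2.3 bootstraps.

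**What to change.** Add a sentence to section 11.2.1, and carry it into the SAP: linear regressions comparing PUL with the SNDS cohort use heteroscedasticity-consistent (HC3) standard errors that respect the matched sets, or a bootstrap that resamples whole matched sets, whatever the count. The unadjusted tests need no change on this account.

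The change costs protocol and SAP wording and a little programming, with no additional data or patients. If the variances prove equal, the loss of efficiency is negligible. With strongly skewed costs and 80 PUL men, some excess error may remain: the unequal-variance test reached 6.5% in the worst simulated case, against 20% or more for the default.

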	a description of the associated complications.		
	Comparisons between the PUL and the TURP/Laser cohorts and between the PUL and the SNDS cohorts will be performed after 1 year and 3 years of follow-up in a intention-to-treat analysis using:		
	o a linear regression model when it involves quantitative variables,		
	 a logistic regression model adjusted on potential confounding when it involves qualitative variables. 		
EXPECTED IMPACTS	Results of the study will be used to support French market release, reimbursement, and clinical acceptance of the Urolift system in France.		

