1.3. JUSTIFICATION OF THE METHODOLOGICAL CHOICES

A two-phases economic evaluation

Randomized controlled trials were yet conducted and the remaining question is the cost effectiveness of PUL compared to other transurethral procedure in French daily practice. That's the reason why, we decided to propose an economic evaluation as the primary objective of this study.

In order to provide all pertinent clinical and economical information comparing PUL and TURP/laser surgery over a long-term follow-up period in the French context, we propose to conduct a study in two phases.

1-In the first phase we will prospectively compare a cohort of patients treated with PUL to another cohort of patients treated with TURP/laser during one year follow-up. This part of the study will enable us to gather real-life unknown information on the use of Urolift in French hospitals daily practice and organisation (number of implants needed, length and cost of surgery, length of hospital stay...) and to collect quality of life and clinical data from French population.

2- As some consequences of the surgery, as well as differences between healthcare consumptions, can occur even after 4 months and 1 year, and because it is difficult to pursue the clinical trial over 1 year without too many lost for follow-up patients, we decided to work on health databases for the second part of this study. This second phase will cover a 3-years follow-up by analysing healthcare resources utilization in each cohort using the French nationwide claims database, the SNDS. The comparison between PUL and TURP/Laser procedures will be strengthened by a complementary analysis performed between the PUL cohort and a matched cohort of patients identified in the SNDS database with the same baseline characteristics but treated with transurethral procedures. The matching process (based on a hdDRS) and the statistical methods of adjustment will overcome the absence of randomization in the initial process of patients' assignment to the PUL or TURP cohort.

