1.4. RISK/BENEFIT RATIO

PUL surgery is a mini-invasive alternative to BPH standard surgery, which is intended to avoid post-operative complications and some long-term side effects, while keeping a reasonable efficiency to treat LUTS. The post-operative complications are mainly related to infections and bleeding, and are responsible of the morbidity of the BPH surgery. The persistent complications as urinary incontinence strongly affect the long-term quality of life.

Performing PUL surgery may decrease the risk of post-operative complications related with infections and bleeding. Performing PUL surgery may decrease the risk of the persistent urinary and sexual side effects and preserve quality of life.

Performing PUL surgery may be less effective than standard surgery in terms of LUTS treatment.

Performing PUL surgery may lead to earlier relapse of LUTSs compared to standard surgery.

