2.2. SECONDARY OBJECTIVES

To assess the incremental cost/effectiveness ratio of PUL compared with transurethral surgery at 12 months.

The secondary objectives will be also to compare between the PUL and the transurethral procedures:

- The real cost of hospitalization related to each surgery procedure from the hospital point of view
- The overall and specific urogenital healthcare consumptions at 4 months, 1 year and 3 years following the surgical procedures;
- The BPH retreatment (including medical and surgical treatments) at 1 and 3 years after surgical procedures;
- The urinary symptoms at 4 months and 1 year after surgical procedure;
- The global quality of life, including sleep comfort at 4 months and 1 year after surgical procedures;
- The time to complete recovery and to return to normal professional activities evaluated at 1, 2, 3 and 4 months:
- The sexual side effects at 4 months and 1 year after surgical procedures;
- The complications associated with the surgical procedures at 4 months after surgical procedures.

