11.2.4. SECONDARY CRITERIA

The following analyses will be performed for each cohort, according to the matched treatment group:

- An estimation of the total hospital cost of each surgery procedure based on a top down micro-costing method performed during hospitalization stay;
- A description of the overall and specific urogenital healthcare consumptions during the 3 years of follow-up;
- A description of BPH re-treatment over the 3 years of follow-up (number of patients with a new BPH medication, number of patients hospitalized for BPH surgical procedure);
- A description of urinary symptoms (value of the IPSS, ISI, ICIQ-UI SF scores during the 1st year of follow-up and number of patients with hospitalization for urinary infection, for urinary retention, or for urethral stricture during the 3 years of follow-up);
- A description of the quality of life during the 1st year of follow-up using the IPSS-Q8 score, the Jenkins sleep questionnaire, the EQ-5D-5L questionnaire;
- A description of the recovery after surgery using the Quality of Recovery visual analogue score and the time before returning to normal professional activities;
- A description of the sexual side effects during the 1st year of follow-up using the IIEF15 and MSHQ-EjD questionnaire;
- A description of the associated complications (number and types).

[figure not shown]
A detailed analysis plan will be defined and will be validated by the steering committee of the study. Subsequent modifications must be made before the blinding is lifted on the database and will be systematically validated by the Scientific Council.

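### For dated secondary events, the only time-based comparison of PUL with TURP/laser is an unadjusted log-rank test; the adjusted model answers only the fixed 1- and 3-year questions

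*Protocol*

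**What the plan says.** Protocol section 11.2.1 gives two rules that both reach the same events.

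- Time-based rule: "Occurrence of events (retreatment, urinary symptoms) will be estimated across time using Kaplan-Meier estimator and compared between groups with logrank test". No covariates or strata are named, and the two-sided 5% level stated there covers all tests.
- Adjusted rule, for PUL v TURP/laser and for PUL v SNDS: linear regression for quantitative outcomes, and for the rest "using logistic regression model adjusted on potential confounders when it involves qualitative variables". The synopsis (data analysis) repeats it: "a logistic regression model adjusted on potential confounding when it involves qualitative variables".

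The outcomes are set at fixed horizons. Section 2.2 lists "The BPH retreatment (including medical and surgical treatments) at 1 and 3 years after surgical procedures". Section 3.2 puts hospitalisations for urinary infection, retention and stricture at the same two horizons. Section 11.2.4 plans "A description of BPH re-treatment over the 3 years of follow-up" as numbers of patients.

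On confounding, section 1.3 says that the matching and the "statistical methods of adjustment will overcome the absence of randomization in the initial process". The matching belongs to the SNDS cohort only (section 5.2.3): "A total of 5 patients will be matched to 1 patient of the PUL cohort for each procedure (TURP, HLE, GLV"). On timing, section 1.4 states: "Performing PUL surgery may lead to earlier relapse of LUTSs compared to standard surgery".

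**The concern.** Patients and surgeons choose the procedure, and in the clinical phase the groups also differ by surgeon. The protocol's answer is adjustment, but the one comparison that uses event dates is not adjusted. The adjusted comparison reduces each man to event or no event by 1 or 3 years, so it cannot separate retreatment at month 13 from retreatment at month 35.

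For PUL v TURP/laser, whether men relapse earlier after PUL would then be tested at the 5% level with no confounding control. Retreatment bears on the durability argument in a file meant to support reimbursement. A report could show a log-rank p-value and an adjusted odds ratio that disagree, with no adjusted time-to-event result to set beside them.

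**Working it through.** **Figures in the plan.** The protocol gives no event count, hazard ratio (HR) or power for these events. The nearest figures are the precision statements in section 11.1, and they reproduce. With n = 80, 1.96 × √(p(1−p)/n) is 6.6% at p = 10% and 11.0% at p = 50% (stated: 7% and 11%). 1.96 × CV/√n is 13.2% and 26.3% for CV 0.6 and 1.2 (stated: 13% and 26%). The matched cohort is 80 × 5 × 3 = 1,200, as stated.

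**Which comparison has which protection, as written**

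| Comparison | Log-rank (uses dates) | Logistic (1 and 3 years) |
|---|---|---|
| PUL v TURP/laser | no adjustment, no matching | adjusted |
| PUL v SNDS | no adjustment; matched on age, month and disease risk score | adjusted, after matching |

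The top left cell is the gap.

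**Size by hand.** Assumptions, not from the protocol: one prognostic factor with HR 1.6 per SD, imbalanced by 0.5 SD; 3-year risk 30% at the covariate mean in the TURP/laser group; 80 per group; no true effect; no loss.

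- Spurious log HR: 0.5 × ln 1.6 = 0.235 (HR 1.26).
- Averaged over the factor, 3-year risks are 31.7% and 37.9%, so events = 80 × (0.317 + 0.379) ≈ 55.6.
- SE of the log HR ≈ 2/√55.6 = 0.268, so the shift is 0.235/0.268 = 0.88.
- Rejection = P(Z > 1.96 − 0.88) + P(Z < −1.96 − 0.88) ≈ 14.2%.

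**Size by simulation**, no true effect, imbalance 0.3 to 0.5 SD, 80 v 80:

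| Inputs (assumed) | Unadjusted test | Adjusted Cox | Adjusted logistic |
|---|---|---|---|
| HR 1.6 per SD; risk 10% or 30%; loss 0% or 15%; 600 runs | 5.2–14.2% | 2.5–6.5% | 3.0–6.2% |
| HR 1.5 per SD; events 20% or 40%; loss 6%; 1,500 runs, done twice | 5.4–12.4% | 3.9–5.5% | 4.1–5.1% (second run only) |

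The hand case is the 14.2% cell. The Monte Carlo standard error near 5% is √(0.05 × 0.95/600) = 0.9 points for 600 runs and 0.6 points for 1,500.

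**Power, Cox v logistic** (true HR 2, 80 v 80). With no loss: 0.36 to 0.38 for each at 10% risk; 0.80 to 0.83 v 0.78 to 0.81 at 30% risk. With 15% loss at 30% risk: 0.75 to 0.78 v 0.70 to 0.74. With complete follow-up the two are nearly equal.

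**Scale.** Under proportional hazards the odds ratio (OR) and HR differ by arithmetic:

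- 40% v 25%: OR = (0.40/0.60)/(0.25/0.75) = 2.00; HR = ln 0.60/ln 0.75 = 1.78.
- 55% v 40%: OR 1.83; HR 1.56.
- 13.6% v 5%: OR 2.99; HR 2.85.

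**The case against.** The strongest case against is that an adjusted analysis already exists and fits the endpoints as defined. Retreatment and urinary hospitalisation are set at 1 and 3 years, and with complete follow-up an adjusted comparison of those proportions is legitimate. In the simulations it controls confounding as well as Cox. This stands, and four stronger readings fall with it or for related reasons.

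- A reader might infer that these events are compared without any adjustment, or that logistic regression leaves confounding that Cox would remove. Neither is so: the inflation belongs to the unadjusted test.
- A reader might infer that the odds ratio is biased. It is another measure, and the protocol nowhere reads it as a rate ratio.
- A reader might infer that every log-rank test here lacks confounding control. The one against the SNDS cohort follows matching, so it has some by design.
- A reader might infer that the logistic model mishandles censored men throughout. The synopsis and section 5.1.2 keep only PUL and TURP/laser men with a full 3-year follow-up, so in those cohorts there is little censoring as written. The question becomes one of selection: men who die or leave the database are dropped because of what happens after the procedure. The SNDS criteria (sections 5.2.1 and 5.2.2) state no such rule.

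It can also be said that the section is general, that an SAP is promised, and that nothing forbids adding an adjusted survival model. That lowers the weight. But the point concerns methods that the protocol names for these events, with the adjusted one repeated in the synopsis; an SAP that simply follows them would carry the gap forward.

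**Conclusion.** The point holds as a modest improvement to secondary outcomes. For PUL v TURP/laser, the protocol's only comparison of when retreatment and urinary hospitalisations occur has no confounding control, while its adjusted model does not address timing. With a 0.3 to 0.5 SD imbalance in one factor of HR 1.5 to 1.6 per SD, the unadjusted test would reject a true null in about 5 to 14% of trials, against 2.5 to 6.5% after adjustment by either model. These inputs are assumed: a smaller imbalance or a weaker factor brings the excess towards zero, and several factors leaning the same way would raise it. The primary cost-effectiveness outcome is not touched.

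**What to change.** In section 11.2.1 and in the synopsis:

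1. For dated events (BPH retreatment, urinary hospitalisations), make a covariate-adjusted time-to-event model the between-group comparison: Cox with the confounders used in the logistic model, accounting for the matched sets in PUL v SNDS.
2. Report adjusted event probabilities at 1 and 3 years, which match the stated horizons.
3. Label Kaplan-Meier curves and the unadjusted log-rank test as descriptive. The adjusted logistic model at 1 and 3 years may stay as a supporting analysis, and logistic regression remains the method for categorical outcomes without a date.
4. State whether death is a censoring or a competing event.
5. Reconcile this with the full 3-year follow-up rule in the synopsis and section 5.1.2, which selects on follow-up after the procedure and sits badly with any time-to-event analysis.

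The cost is wording and some analysis time; section 6 shows that the SNDS holds the dates of dispensing and hospital care. There are two real downsides. Section 1.1.2.1 places most surgical complications in the first 3 months, while the concern with PUL is later relapse, so hazards may not be proportional; the check matters and a single hazard ratio may need to be split by period. Under the data protection rules in section 15, death is kept only to month and year, so a convention for the day is needed.
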